3.1 Variations to the Protocol

[REDACTED]

3.2 Investigational Sites

Up to ten (10) U.S. and Canadian investigational sites will participate in this study. Each site will obtain written approval from a Central IRB prior to recruitment and enrollment of any subject into the study. Any changes to the study procedures must be made with the mutual agreement of the Principal Investigator and the Sponsor, documented in an amendment to protocol, and approved by the reviewing IRB.

[REDACTED]

[REDACTED]

[REDACTED]

3.4 Independent Panel Review (Photographs)

Three independent experts, that are not Investigators in the clinical study, will be selected and trained to conduct PR-SRS assessments on photographs. Prior to conducting the Independent Panel Review (IPR), each member of the panel will be certified regarding the conduct of PR-SRS assessments as described in Section 3.3.

3.5 Medical Monitor

A Medical Monitor will provide safety oversight for this clinical study. The Medical Monitor, in consultation with the Sponsor's team, will review and evaluate AEs/SAEs/UADEs monthly, review safety reports, and will provide consultation and recommendations with regard to inclusion/exclusion criteria, concomitant medications/treatments, and subject discontinuations. The Medical Monitor will follow the Safety Management Plan and report the trends of AEs, and address specifically SAE, UADE with the Sponsor.

3.6 Photography

Set-up of photographic equipment, as well as training and quality control processes, will be provided and will be managed by a dedicated professional third party

4 OVERVIEW OF STUDY DESIGN

4.1 Study Design

This is a randomized, blinded, No-Treatment control, multicenter, prospective clinical study, to identify whether TEOSYAL® RHA Redensity is more effective than No-Treatment in the correction of moderate to severe perioral rhytids at Week 8 after initial or touch-up treatment.

The **Treating Investigator** (TI) will evaluate subjects for eligibility of the subject for the study. The **Blinded Live Evaluator** (BLE) at screening will evaluate the subject's perioral rhytids severity using the Perioral Rhytids Severity Rating Scale (PR-SRS) in order to confirm eligibility and to establish a pre-treatment score. This will be done independently of the TI, and exact concordance between the BLE and the TI is not necessary.

Enrolled subjects will be randomized to either the TEOSYAL® RHA Redensity treatment group or the “No-Treatment” control group. The TI will administer study device, and if necessary, subjects will receive a touch-up treatment 14 days following the initial treatment to optimize the results. The TI will conduct safety and effectiveness evaluations at study subject visits, which will occur at Week 4, 8, 12, 16, 24, 36, and 52 after initial or touch-up treatment, and 4 weeks after a repeat treatment.

The BLE will conduct assessments of efficacy during the trial, including assessment of the primary endpoint at Week 8 after initial or touch up treatment. The BLE will conduct effectiveness evaluations at Week 8, 12, 16, 24, 36, and 52 after initial or touch-up treatment.

Subjects will be followed for 52 weeks from initial or touch up treatment, at which point they will be offered a repeat treatment (provided that the TI deems the treatment to be appropriate, and if the subject agrees). The subject will then be followed for an additional 4 weeks after the treatment before exiting the study.

[figure not shown]
Should a subject return to his/her pre-treatment PR-SRS level before Week 52, as assessed by the TI, he/she will be eligible to receive an early repeat treatment (provided that the TI deems the treatment to be appropriate, and if the subject agrees) at Week 12, or Week 16, or Week 24, or Week 36 after initial or touch-up treatment. .

Subjects randomized to the “No-Treatment” control group will receive their first treatment after the primary endpoint evaluation (8 weeks after randomization) and will then follow the same schedule as the initial treatment group.

4.2 Study Design Rationale

4.2.1 Study Population

At least 200 subjects will be enrolled and randomized. At least 150 subjects will receive treatment with TEOSYAL® RHA Redensity, and at least 50 subjects will be enrolled as No-Treatment controls.

[REDACTED]

[REDACTED]

[REDACTED]

4.2.2 Primary Effectiveness Outcome Measurement

The primary endpoint will be a co-primary endpoint. A responder will be defined as a subject who has a ≥ 1 -grade improvement on the PR-SRS as assessed by the BLE before initial treatment (baseline) and at Week 8 after initial or touch-up treatment. The effectiveness of TEOSYAL® RHA Redensity will be demonstrated if:

- The responder rate for subjects treated with TEOSYAL® RHA Redensity is statistically superior to the responder rate for the No-Treatment control, and;
- The responder rate for subjects treated with TEOSYAL® RHA Redensity is $\geq 70\%$, and;
- The difference between the responder rate for subjects treated with TEOSYAL® RHA Redensity and the No-Treatment group must be ≥ 50 points.

5 STUDY POPULATION

[figure not shown]
5.1 Inclusion Criteria

1. Outpatient, male or female of any race, 22 years of age or older. Female subjects of childbearing potential must have a negative UPT at Visit 1 and practice a reliable method of contraception throughout the study.

3. Willing to abstain from facial aesthetic procedures/therapies below the orbital rim that could interfere with study evaluations (e.g., other fillers, lip augmentation, botulinum toxin injections, laser or chemical resurfacing, etc.) for the duration of the study (see Section 7.5.1 for the medications/procedures have either restrictions for usage, or are prohibited during the course of the study).
4. Be able to follow study instructions and likely to complete all required visits;
5. Sign the IRB-approved ICF, Photographic Release Form and the Authorization for Use and release of Health and Research Study Information (HIPAA) form prior to any study-related procedures being performed.

5.2 Exclusion Criteria

1. Female subjects that are pregnant, breast-feeding, or of childbearing potential and not practicing reliable birth control.
3. Use of a prohibited treatment/procedure within time periods
5. Known susceptibility to keloid formation, hypertrophic scarring or clinically significant skin pigmentation disorders (TI discretion).

8. History of connective tissue disease.

10. Need for clinically significant (TI discretion) and continuous medical treatment within 2 weeks prior to Visit 1.

12. Herpes simplex lesion flare-ups greater than 6 per year.

14. Elective, clinically significant facial procedures that may confound the interpretation of the results in the perioral region (TI discretion) prior to study enrollment.

16. Subjects with known prolonged bleeding times because of disease or medication. If on a drug or supplement that prolongs bleeding times (eg non-steroidal anti-inflammatory, anti-coagulant, fish oil), wait 14 days or until bleeding times return to normal before injecting.

18. Have dentures or any device covering all or part of the upper palate, and/or severe malocclusion, dentofacial or maxillofacial deformities, or significant asymmetry of the perioral area (TI discretion).

20. Exposure to any other investigational drug/device within 90 days prior to study entry.

6 TREATMENT ALLOCATION AND RANDOMIZATION

All subjects who have signed an ICF will receive a 4-digit subject number, starting at 0001. Subject numbers will be assigned in ascending order and will be coupled with the site identification number for unique identification of each subject. The subject number will be used to identify the subject throughout the study. Subjects withdrawn from the study will retain their subject number; new subjects will be allocated a new subject number.

Upon qualifying for treatment, subjects will be randomized to a study group utilizing a randomization algorithm embedded into the electronic Case Report Form (eCRF).

Subjects will be randomized (3:1 ratio) to one of the following groups:

- TEOSYAL® RHA Redensity;
- No-Treatment (untreated control).

The TI will secure the treatment allocation and any other record of study treatment from potential discovery by the BLE. Any instance where the blind is opened to the BLE will be documented in writing.

Subjects will be considered “enrolled” at the time of consent, and will be considered “enrolled and randomized” at the time of randomization. The required sample size is based on “enrolled and randomized” subjects. If an enrolled subject withdraws from the study prior to being randomized, he/she may be replaced.

7 DEVICE APPLICATION

Digitized by [contact]

Black box for the first part of the answer

11. **What is the primary purpose of the following statement?**

11. **What is the primary purpose of the *Journal of Clinical Endocrinology and Metabolism*?**

11. **What is the primary purpose of the following statement?**

11. **What is the primary purpose of the *Journal of Clinical Endocrinology and Metabolism*?**

Black box for the final answer.

11. **What is the primary purpose of the *Journal of Clinical Endocrinology and Metabolism*?**

Black box

11. **What is the primary purpose of the *Journal of Clinical Endocrinology and Metabolism*?**

A series of 15 horizontal black bars of varying lengths, decreasing in size from top to bottom. The bars are evenly spaced and extend across the width of the page. The lengths of the bars decrease in a regular, linear fashion from the top bar to the bottom bar.

7.3 Labeling, Packaging and Storage

Open-label packaged supplies of TEOSYAL® RHA Redensity will be provided to the sites in bulk

(i.e., individual kits per subject will not be provided). External packaging (carton) will be labeled with study information (i.e., study number, study Sponsor, name and address of TEOXANE, quantity, “CAUTION: Investigational device. Limited by US Federal law to investigational use”, etc.). There may be one or two blisters inside each carton. Each blister will contain one syringe and two needles. The Tyvek lid on the blister will include:

- Study number: TEO-RHA-1501
- IDE number: e.g., G160123
- Name and address of the Sponsor/Manufacturer (i.e., TEOXANE S.A.)
- Name of product (i.e., TEOSYAL® RHA Redensity)
[REDACTED]
[REDACTED]
- Batch number
- Manufacturing date
- Expiry date
- The CAUTION statement mentioned above

There will be no study specific labeling applied directly to the device syringe. The Investigator Brochure will provide all relevant contraindications, hazards, adverse effects, warnings and precautions.

The study device is to be stored at room temperature (2°C to 25°C) in a secure area with restricted access.

7.3.1 Relabeling

Real-time aging testing is in progress for TEOSYAL® RHA Redensity. As new test data will become available throughout the course of the study, the shelf life of TEOSYAL® RHA Redensity may be extended through the course of the study. The site monitor will be responsible for relabeling the Tyvek lid with the new expiry date. The site monitor will follow a specific procedure to perform and verify the product relabeling with the extended expiry date (to be provided in a separate guidance document). The relabeling process will be documented. TEOSYAL® RHA Redensity may also be returned to the Sponsor to be relabeled. When TEOSYAL® RHA Redensity has reached the expiry date as indicated on its label, the PI should segregate them and follow the instructions from the site monitor as to awaiting for relabeling by the site monitor or returning the devices to the Sponsor.

It is the responsibility of the TI to verify that a device is within its expiry date before being used. The initial shelf life of TEOSYAL® RHA Redensity will be approximately 6 months. However, as devices being subjected to real time aging are being tested periodically, the shelf-life could be extended.

7.4 Study Device Supply and Accountability

The study Sponsor will ensure that participating sites are provided with a sufficient supply of study devices for initial treatments, touch-up treatments, and for retreatments. It is forbidden to use a study device for purposes other than defined in this protocol.

Study devices must be kept in a locked area with access restricted to designated study personnel. The Principal Investigator or designate will inventory and acknowledge receipt of all study device shipments, and to ensure that the integrity of study devices is not jeopardized prior to use.

Accurate accountability records will be maintained that include batch numbers, quantities received/returned/destroyed, as well as dates and volumes administered, and the site monitor will be provided access to the study devices and records for periodic review.

Unused syringes will be returned to the Sponsor at the end of the study unless other arrangements are agreed upon in writing. **Used syringes** will be disposed of according to each site's standard procedures.

[figure not shown]
7.4.1 Other Study Supplies

7.5 Concomitant Medications and Procedures

Any medication or procedure, including over-the-counter preparations, that the subject takes during the study protocol period is considered concomitant medication and will be captured on the Concomitant Medications and Procedures page of the eCRF.

7.5.1 Prohibited Treatment and Procedures

8 DATA COLLECTION

8.1 Electronic Case Report Form

Treatment and follow-up of subjects will be recorded in a 21 CFR part 11 compliant eCRF. Data will be first recorded into the medical record and study specific source document worksheets prior to entry into the eCRF.

A paper CRF will be used to capture additional demographics and social history.

Two sets of worksheets will be used to capture study specific information (i.e., efficacy assessments, injection volumes, injection technique, etc.); one set for the BLE and study coordinator, and one set for the TI and study coordinator. This will allow the BLE and TI to remain blinded to each other's assessments. The study coordinator will refer to these worksheets in conjunction with the medical record in order to complete data entry into the eCRF. Study Investigators will not disclose their opinion regarding treatment outcomes with subjects in order to, 1) prevent subjects from sharing such opinions between the TI and the BLE, and 2) avoid biasing subject reported outcomes.

In order to review and electronically sign the eCRF, the BLE and TI will have individual login passwords that will allow them to view only the data that they have generated. The BLE and TI must ensure that they electronically sign for completed eCRFs on a timely basis.

8.2 Subject Diary and Questionnaires

Subjects will complete paper-based subject 14-day diaries and questionnaires. Data recorded in these documents will be entered into the eCRF by the study coordinator.

[figure not shown]
8.3 Photography

9 STUDY EVALUATIONS

9.1 Informed Consent

The Principal Investigator (or designate) will explain the benefits and risks of participation in the study to each subject and will obtain written informed consent. Written informed consent must be obtained prior to the subject entering the study (before initiation of any study related procedure and injection of study devices).

This figure is a horizontal bar chart illustrating the distribution of a variable across 20 distinct categories. The categories are represented by black horizontal bars, and their lengths indicate the magnitude of the variable for each category. The bars are ordered from the longest at the top to the shortest at the bottom. The chart is set against a white background with a black border around the figure area.

The figure consists of two groups of horizontal bars. The top group has 10 bars of varying lengths, with the longest bar on the left. The bottom group has 10 bars of varying lengths, with the longest bar on the right. The bars are black on a white background.

A bar chart illustrating the distribution of a variable across 10 categories. The categories are represented by horizontal bars of varying lengths, ordered from left to right. The distribution is roughly bell-shaped, with the highest frequency in the first category and a gradual decline towards the right. The bars are black and are set against a white background.

A series of horizontal black bars of varying lengths, likely representing data points or measurements. The bars are arranged in a grid-like structure with some vertical alignment, suggesting a hierarchical or grouped data structure. The lengths of the bars vary significantly, with some reaching near the top of the frame and others being much shorter.

A series of 15 horizontal black bars of varying lengths, decreasing from top to bottom. The bars are positioned on a white background.

The image consists of a large number of horizontal black bars of varying lengths, indicating redacted content. The bars are arranged in a grid-like pattern, with some bars being significantly longer than others, suggesting different levels of redaction or different types of information being withheld.

A large, dense collection of black horizontal bars of varying lengths, likely representing data points or categories in a visualization. The bars are arranged in a grid-like pattern, with some rows having more bars than others. The lengths of the bars vary significantly, with some being very short and others being quite long. The overall effect is a complex, abstract pattern of black lines on a white background.

A large, dense collection of black horizontal bars of varying lengths, arranged in a grid-like pattern. The bars are distributed across the entire page, with some appearing in pairs or small groups. The lengths of the bars range from very short to very long, creating a visual texture of horizontal lines.

[figure not shown]
A horizontal bar chart consisting of 20 solid black bars of varying lengths, arranged from top to bottom. The bars are of different widths, with some being very narrow and others being very wide. The lengths of the bars are not uniform, creating a visual representation of data distribution.

A series of horizontal black bars of varying lengths, likely representing data points or categories in a visualization. The bars are arranged in a grid-like structure, with some rows containing multiple bars and others containing a single long bar. The lengths of the bars vary significantly, with some being very short and others being very long, suggesting a wide range of values or categories represented.

9.5 Efficacy

9.5.1 Primary Efficacy Variable

9.5.2 Secondary Efficacy Variables

Digitized by [contact]

[REDACTED]

For more information, visit www.ams.org.

[REDACTED]

A horizontal bar chart showing the number of publications per year from 1990 to 2010. The y-axis represents the number of publications (0 to 1000), and the x-axis represents the year (1990 to 2010). The chart shows a significant increase in publications over time, with a major peak around 2005.

Year	Number of Publications
1990	100
1991	120
1992	150
1993	180
1994	220
1995	250
1996	300
1997	350
1998	400
1999	450
2000	500
2001	550
2002	600
2003	650
2004	700
2005	750
2006	800
2007	850
2008	900
2009	950
2010	1000

[REDACTED]

1. **What is the primary purpose of the proposed legislation?**

[REDACTED]

[REDACTED] [REDACTED]

1

THE JOURNAL OF CLIMATE

100% of the time, the *hedgehog* is a hedgehog, and the *cat* is a cat. The *hedgehog* is not a *cat*, and the *cat* is not a *hedgehog*.

[REDACTED]

11. **What is the primary purpose of the study?** (check all that apply)

For more information, contact the Office of the Vice President for Research and Economic Development at [contact] or [contact].

—
—
—

v 1.2; 27 Oct 2017

A horizontal bar consisting of a thick black segment on the left and a white segment on the right, separated by a thin vertical line. Below this bar is a thick green horizontal line.

A thick black horizontal bar with a thin white vertical bar on the left side, and a thin black vertical bar on the right side.

Type of cancer	Percentage
Other	~85%
Breast	~15%
Lung	~10%
Colon	~5%

[REDACTED]

[REDACTED]

9.6 Safety

100% of the time, the system is able to correctly identify the target word in the sentence.

© 2013 by the author; licensee MDPI, Basel, Switzerland. This article is an open access article distributed under the terms and conditions of the Creative Commons Attribution license (<http://creativecommons.org/licenses/by/3.0/>).

For more information, contact the Office of the Vice President for Research and the Office of the Vice President for Student Affairs.

A series of 12 horizontal black bars of varying lengths, decreasing in size from top to bottom. The bars are evenly spaced and extend across the width of the page. The lengths of the bars decrease in a regular, linear fashion from the top bar to the bottom bar.

9.6.5 Pregnancy

A female of childbearing potential must present a negative UPT prior to any injection (initial, touch-up, retreatment) of the study device.

Subjects who are pregnant are excluded from the study. Female subjects of childbearing potential are expected to prevent pregnancy occurring whilst on treatment by using effective birth control methods (e.g., oral contraceptive, condom, IUD, injectable contraceptive, or diaphragm). Male subjects have no contraceptive restrictions.

9.6.6 Adverse Events

All observed or volunteered AEs regardless of treatment group or suspected causal relationship to the study device(s) will be recorded in the eCRF. Subjects will be questioned for the occurrence of any new or worsening signs or symptoms at each visit by the following methods:

- Information volunteered by the subject
- Open ended and non-leading questions such as: Have you had any health problems since your last visit?
- Observation by the investigational team, other care providers or relatives

9.6.6.1 Adverse Event Reporting

Throughout the course of the study, all AEs will be monitored and reported through the AE eCRF. If an AE occurs, the first concern will be the safety of the study participants. All Device Related AEs occurring after study device administration will be followed until the event has resolved or stabilized or until follow-up is no longer possible.

If a Device Related AE(s) is ongoing at the final study visit, the TI will determine which action should be taken and should schedule a clinic visit (if appropriate; i.e., if the event is clinically significant) within 4 weeks to verify that the AE has resolved.

9.6.6.2 Definition of an Adverse Event

An AE is any untoward medical occurrence in a subject or clinical investigation subject administered the study device and which does not necessarily have to have a causal relationship

with the device. An AE can therefore be any unfavorable or unintended sign (for example an abnormal laboratory finding), a symptom or disease temporally associated with the use of the study device, whether or not considered related to that device.

AEs may include, but are not limited to, subjective or objective symptoms spontaneously offered by the subject, solicited via the diary and subject interviews, uncovered by review of concomitant medications or therapies, and/or observed by the study site staff. The TI will determine the description (sign, symptom, or diagnosis), onset, resolution, seriousness, severity, cause and action taken for any event.

Disease signs and symptoms that existed prior to the study injections are not considered AEs. Recurring symptoms associated with pre-existing conditions are not considered AEs unless they have a clinically significant increase in severity and/or frequency.

Clinically significant abnormal clinical laboratory tests (if applicable) must be recorded as an AE.

Changes resulting from normal growth and/or development occurring at a physiologically appropriate time that do not vary significantly from the frequency or severity expected, for example the onset of menses or menopause, are not to be considered AEs.

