2 STUDY OBJECTIVES

The study objectives are to establish the safety and effectiveness of TEOSYAL® RHA Redensity in the treatment of moderate to severe perioral rhytids:

1. To demonstrate the superiority of TEOSYAL® RHA Redensity versus the No-Treatment control at 8 weeks for the correction of moderate to severe perioral rhytids. Assessment of superiority will be based on the Perioral Rhytids Severity Rating Scale (PR-SRS) as rated by the Blinded Live Evaluator (BLE) at each investigative site.
2. To evaluate the safety of TEOSYAL® RHA Redensity for the treatment of moderate to severe perioral rhytids. Safety will be determined by the rates of Adverse Events (AEs) associated with the use of the study device. Subjects will be observed for up to approximately 52 weeks following initial treatment or touch-up treatment with the study device. Safety will also be evaluated for 4 weeks following any retreatment.

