9.6.6.4 Causality Assessment

The TI's assessment of an AE's relationship to the study device is part of the documentation process, but it is not a factor in determining what is or is not reported in the study. If there is any doubt as to whether a clinical observation is an AE, the event will be reported. The TI will assign the causality assessment according to his/her clinical experience and the subject's description of the event. The Sponsor will be responsible for the final causality judgment. The causal relationship should be classified according to the following criteria (not all variables need to be present to be indicative of relationship to the device):

Definitely related:

- The temporal sequence of AE onset relative to injection of study device is reasonable.
- The AE is more likely explained by the study device or procedure than by another cause.
- The AE shows a pattern consistent with previous knowledge of the study device.

Probably related:

- The temporal sequence of AE onset relative to injection of study device is reasonable.
- The AE is more likely explained by the study device or procedure than by another cause.

Possibly related:

- The temporal sequence of AE onset relative to injection of study device is reasonable.
- The AE could have been due to another equally likely cause.

Probably not related:

- There is another more likely cause of the AE.

Definitely not related:

- The temporal sequence of AE onset relative to injection of study device is not reasonable.
- There is another obvious cause of the AE.

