11.8 Safety Analysis

[REDACTED]

[REDACTED]

The study will be able to detect any AE that has an incident rate of <1.0% (0.625%) or more (assuming 200 subjects will be treated with the investigational device in the two pooled arms and taking [REDACTED]

[REDACTED]

[REDACTED]

[REDACTED]

[REDACTED]

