#### 3.2 Exclusion Criteria

1. Female subjects that are pregnant, breast-feeding, or of childbearing potential and not practicing reliable birth control.

3. Use of a prohibited treatment/procedure within time periods

5. Known susceptibility to keloid formation, hypertrophic scarring or clinically significant skin pigmentation disorders (TI discretion).

[REDACTED]

7. History of active chronic debilitating systemic disease that in the opinion of the investigator, would make the subject a poor candidate in the study.

[REDACTED]

9. Malignancy (excluding non-melanoma skin cancer) within the past 5 years.

[REDACTED]

11. History or presence of condition or feature that may confound the interpretation of the results in the perioral region, for example, tattoo, significant facial hair, acne scarring, prior surgery in the area, potential for active disease or infection flare up such as herpes simplex.

[REDACTED]

13. History of skin cancer in the treatment area.

[REDACTED]

15. Clinically active disease or infection in the perioral area or mouth (e.g., dental abscess).

[REDACTED]

17. Medical or psychiatric conditions that may increase the risk associated with study participation or may interfere with the interpretation of study results or compliance of the subject and, in the judgment of the Investigator, would make the subject inappropriate for entry into this study (TI discretion).

[REDACTED]

19. Subjects seeking lip augmentation.

[REDACTED]

21. Clinically significant alcohol or drug abuse, or history of poor cooperation or unreliability.

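### The adverse event definition lets a usual-severity perioral flare of a pre-existing condition, such as herpes simplex, go unrecorded after a study injection

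*Protocol*

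**What the plan says.** Protocol 9.6.6.2 opens with a broad definition of an adverse event, which takes in "a symptom or disease temporally associated with the use of the study device, whether or not considered related to that device". It then narrows it: "Recurring symptoms associated with pre-existing conditions are not considered AEs unless they have a clinically significant increase in severity and/or frequency".

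Other passages bear on how this works in practice:

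- Protocol 9.6.6, on visits: "Subjects will be questioned for the occurrence of any new or worsening signs or symptoms at each visit".
- Protocol 9.6.6.4: "If there is any doubt as to whether a clinical observation is an AE, the event will be reported". The same section says that the investigator's view of relatedness does not decide what is reported.
- Protocol 5.2, exclusion 12: "Herpes simplex lesion flare-ups greater than 6 per year".
- SAP 3.2, exclusion 11, which covers features that could confound perioral results, gives as one example "potential for active disease or infection flare up such as herpes simplex". SAP section 1 says that the SAP prevails where the two documents differ.
- Protocol 2, on the safety objective: "Safety will be determined by the rates of Adverse Events (AEs) associated with the use of the study device".
- Protocol 11.8: "The study will be able to detect any AE that has an incident rate of <1.0% (0.625%) or more". The synopsis and Protocol 11.5 give 2.5% as the corresponding rate for Fitzpatrick skin types IV to VI.

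**The concern.** The device is injected around the mouth, and the plan itself names herpes simplex as a condition that can flare there. The recurrence sentence is a specific carve-out from the general definition. It asks only whether the episode is worse or more frequent for that person, not where it occurs or whether it follows an injection.

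An investigator who sees a typical cold sore some days after an injection, in a subject with a known history, can apply that sentence as written and record nothing. The event is then lost to every later safety count. Treatment-related events in SAP 9.2.1 and unexpected device effects in Protocol 9.6.6.3 are both defined as subsets of adverse events, so something screened out at the definition is never rated for relatedness. With up to ten sites, different investigators may also resolve the same case differently. What is at stake is how completely and consistently local events are counted for the safety objective.

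**Working it through.** **1. The plan's own figures.** The synopsis asks for 160 treated subjects and allows for 20% dropout: 160 / (1 − 0.20) = 200, as stated. The detectable rates match one event among those followed:

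- All treated subjects: 1 / 160 = 0.625%, as in Protocol 11.8.
- Fitzpatrick IV to VI, at least 25% of subjects: 0.25 × 160 = 40, and 1 / 40 = 2.5%, as in the synopsis and Protocol 11.5.

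At those true rates the chance of seeing at least one event is 1 − (1 − 0.00625)^160 = 63.3% and 1 − (1 − 0.025)^40 = 63.7%. Detection here means observing a single case. If that one case is not recorded, the event type shows as zero.

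**2. Can the frequency test pick up one flare after an injection?** The documents give no flare rates. As an illustration, assume that flares arise at random at a constant yearly rate r (Poisson), with no device effect. The chance of at least one flare in d days is 1 − exp(−r × d / 365).

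| Assumed flares per year | 14 days | 28 days |
|---|---|---|
| 1 | 3.8% | 7.4% |
| 6 | 20.6% | 36.9% |

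Over a whole year, chance alone often gives more than the usual number. A subject who averages 3 flares has 4 or more in 35.3% of years. A subject who averages 6 has 7 or more in 39.1% of 52-week periods. One flare of usual severity after an injection cannot by itself show that frequency has risen, so the exception for increased frequency will rarely bring it back in.

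**3. Can such subjects be in the trial?** Exclusion 12 removes those with more than 6 flares a year, a limit that has effect only if some subjects with 6 or fewer can enter. SAP exclusion 11, read plainly, could remove many of them. Protocol exclusion 11 and SAP exclusion 12 are not visible, so the documents do not settle who is admitted.

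**4. Do the visible safeguards close the gap?**

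- Visit questioning targets new or worsening signs. A usual flare is neither, although the open-ended question may still bring it out.
- The rule to report in case of doubt helps only where the investigator is in doubt. A known history with a typical flare fits the carve-out directly.
- Because relatedness does not decide reporting, suspecting the injection does not by itself turn the flare into an adverse event.

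No visible text says how a perioral flare after an injection is to be recorded.

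**The case against.** The strongest reply is that several provisions work against omission. A first-ever flare is not a recurrence, and one that is more severe or clearly more frequent is an adverse event under the sentence itself. The general definition covers events linked in time to device use. Protocol 7.5 captures all medication, including over-the-counter products, and 9.6.6.2 names medication review as a source of adverse events, so a treated flare should leave a trace. The doubt rule has real force: if nobody can tell whether frequency has risen, that is arguably doubt, and doubt means report. SAP exclusion 11, with the SAP prevailing, may keep many of these subjects out. The diary and much of the safety text are redacted, so separate capture of lesions cannot be ruled out.

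All of this stands, and it limits the claim. A reader might infer that a herpes flare after an injection is never counted, or that subjects with up to 6 flares a year are definitely enrolled. The documents support neither. Nor does the visible text say that injection triggers flares.

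What the reply does not do is remove the carve-out. It shows that an investigator may record the event, not that the plan requires it.

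**Conclusion.** The point holds as a gap in ascertainment. Under 9.6.6.2 a perioral recurrence of usual severity after a study injection may go unrecorded and unrated unless the investigator judges it worse or more frequent. Exclusions 11 and 12 point in different directions on who with a herpes history may enter, and must be reconciled.

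The size of any under-count cannot be derived. A reader might be tempted to put a number on a downward bias. With assumed inputs of 10 to 40% of 200 subjects with a herpes history (h), 2 to 10% flaring per injection course (q) and 2 to 3 courses (k), the formula 200 × h × (1 − (1 − q)^k) runs from 200 × 0.10 × (1 − 0.98²) = 0.8 to 200 × 0.40 × (1 − 0.90³) = 21.7 subjects, about a 27-fold range. None of these inputs is in the documents. Touch-up and retreatment are conditional, so even the number of courses is not fixed. The formula also treats every flare as unrecorded, whether coincidental or not. It is not an estimate of bias.

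The documents do support a narrower statement: their detection thresholds correspond to single events, so one omitted event of a given type can decide whether that type appears in the results. No sample-size or power figure changes.

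**What to change.** Add to Protocol 9.6.6.2 a sentence to this effect: any recurrence of a pre-existing skin or mucosal condition in the perioral area, including herpes simplex, with onset after a study injection is recorded as an adverse event and rated for causality, whatever its earlier frequency; the same recurrences are recorded in No-Treatment controls over the adverse event period already defined, which starts at consent (Protocol 9.6.7.1, SAP 9.2.1).

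In SAP 9.2.1, tabulate these events by randomized group for the first 8-week phase, and show later post-injection events separately. Give follow-up time beside the counts: a touch-up at 14 days makes that phase 2 + 8 = 10 weeks from first injection, against 8 weeks from randomization in controls. Reconcile exclusions 11 and 12, so that it is clear which subjects with a herpes history can contribute such events.

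The cost is one protocol sentence and a small table. The reported adverse event rate will be slightly higher and will include coincidental flares. The controls give only a rough background rate: about 50 subjects for 8 weeks is 50 × 8 = 400 person-weeks, or 400 / 52 = 7.7 person-years, before any dropout.
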